10.5.4 Patient-reported outcomes

Cushing's syndrome HRQoL questionnaire

A 12-item Cushing's syndrome HRQoL questionnaire (CushingQoL) is implemented in this trial. Raw summative scores are calculated and standardized on a by-patient and visit basis.

Patients who completed 9 or more items at an assessment are considered evaluable for that visit. Standardized scores and their changes from baseline to each scheduled post-baseline assessment will be descriptively summarized.

[figure not shown]
[figure not shown]
Work Productivity and Activity Impairment-General Health (WPAI-GH) questionnaire

[figure not shown]
The WPAI-GH yields four types of scores:

1. Absenteeism (work time missed)
2. Presenteeism (impairment at work / reduced on-the-job effectiveness)
3. Work productivity loss (overall work impairment / absenteeism plus presenteeism)
4. Activity Impairment

WPAI-GH scores are based on 1-item (presenteeism, activity impairment), 2-items (absenteeism) and multiple items (overall work productivity); a score will not be calculated if there is a missing response to the corresponding item. For example, an analysis of absenteeism would include only those subjects with responses to hours missed and to hours worked.

WPAI-GH scores and their changes from baseline to each scheduled post-baseline assessment will be descriptively summarized.

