4.12.1.2 CI for continuous variables

Two sided 95%Confidence Interval for continuous variable will be based on the t-distribution. The respective N, Mean and Standard error are outputted in to a data-step and then the TINV function is used to calculate the Confidence Interval as follows:

```
PROC MEANS DATA=test NOPRINT ;
  VAR age ;
  OUTPUT OUT=xxtmp N=n MEAN=mean STDERR=stderr ;
  RUN ;

  DATA xxtmp1 ; SET xxtmp ;
  lo = mean - ( TINV ( 0.95 , n-1 ) * stderr ) ;
  hi = mean + ( TINV ( 0.95 , n-1 ) * stderr ) ;
  RUN ;
```

5 Statistical methods and data analysis

Categorical data will be presented as frequencies and percentages. For continuous data, mean, standard deviation, median, minimum, and maximum will be presented.

A missing category for categorical data will be presented where applicable. Unless otherwise noted, percentages will be based on the number of patients in the relevant population or subgroup.

Whenever possible, minimum and maximum will be presented to the same precision as the raw data. Mean and median will be presented to one more decimal place and standard deviation to two more decimal places.

Unless noted otherwise, no imputation for missing data will be performed.

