Muscle strength	0=able to stand easily with arms extended, 1=able to stand after several efforts without using arms as assistance, 2=able to stand only by using arms as assistance 3=completely unable to stand	Direct observation of ability to stand unaided. Counts & shifts from baseline.
Striae	0=none, 1=mild, 2=moderate, 3=severe	Investigator interpretation, Counts & shifts from baseline.
Bruising	0=none, 1=mild, 2=moderate, 3=severe	Investigator interpretation, Counts & shifts from baseline.

Similar analyses as defined above will also be performed at all other scheduled post-baseline assessments.

Changes from baseline to Week 12 ,24 and 48 in Cushing Quality of Life scores

A 12-item Cushing's syndrome HRQoL questionnaire (CushingQoL, cf. [Webb et al 2008](#)) is implemented in this trial. Patients who completed 9 or more items at a visit are considered evaluable for that visit.

The list of questions includes the following and are answered using a categorical variable ranging from 1 to 5 (see Table 5-3):

1. I have trouble sleeping (I wake up during the night; it takes me a long time to get to sleep, etc.)
2. I have pain that keeps me from leading a normal life
3. My wounds take a long time to heal
4. I bruise easily
5. I am more irritable, I have sudden mood swings and angry outbursts
6. I have less self-confidence, I feel more insecure
7. I'm worried about the changes in my physical appearance due to my illness
8. I feel less like going out or seeing relatives or friends
9. I have had to give up my social or leisure activities due to my illness
10. My illness affects my everyday activities such as working or studying
11. It's difficult for me to remember things
12. I'm worried about my health in the future

Table 5-3 HRQoL ratings

Answers to HRQoL questions	Rating
'Always' or 'Very much'	1
'Often' or 'Quite a bit'	2
'Sometimes' or 'Somewhat'	3
'Rarely' or 'Very little'	4
'Never' or 'Not at all'	5

Standardized scores and their changes from baseline to Week 12, 24 and 48 will be descriptively summarized.

The standardized scores are calculated as follows:

1. Obtain raw scores, denoted by X, as the sum of all the ratings on all the HRQoL questions for a single patient and the score can range from 12 (worst HRQoL) to 60 points(best HRQoL).Therefore, the lower the score, the greater the impact on HRQoL.
2. Obtain standardized score, Y, for a single patient
 - a.
$$Y = 100 \cdot (X-12) / (60-12) = 100 \cdot (X-12)/48$$

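### CushingQoL forms count as evaluable with 9 of 12 items, but the scoring formula fits only 12, so each unanswered item lowers the score and can take it below 0

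*SAP*

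**What the plan says.** Change in CushingQoL score from baseline to Weeks 12, 24 and 48 is a secondary endpoint (Protocol Table 3-1). The instrument is described as "A 12-item Cushing's syndrome HRQoL questionnaire (CushingQoL", with each item "answered using a categorical variable ranging from 1 to 5"; SAP Table 5-3 makes 1 the worst rating and 5 the best.

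Both documents accept incomplete forms. The SAP says "Patients who completed 9 or more items at a visit are considered evaluable for that visit". Protocol Section 10.5.4 says "Patients who completed 9 or more items at an assessment are considered evaluable for that visit".

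The SAP then scores in two steps. Step 1 is "Obtain raw scores, denoted by X, as the sum of all the ratings on all the HRQoL questions for a single patient", adding that "the score can range from 12 (worst HRQoL) to 60 points(best HRQoL". Step 2 is Y = 100 × (X − 12)/(60 − 12). The one worked example has all 12 items answered.

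For missing data, the general convention in SAP Section 5 is "Unless noted otherwise, no imputation for missing data will be performed". Protocol Section 10.5.1 sets the same default for the secondary efficacy analyses. Neither document makes an exception for CushingQoL items.

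**The concern.** The evaluability rule and the formula do not fit together. The rule deliberately keeps forms with 9, 10 or 11 answers. The formula subtracts 12 and divides by 48, which are the minimum and the width of the range for a 12-item sum only. When items are blank, X is smaller simply because terms are absent, and the formula reads the shortfall as worse quality of life.

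The endpoint is a within-patient change, so the error matters most when the number of answered items differs between visits. Blanks at follow-up create a false worsening and blanks at baseline a false improvement. Because SAP Section 5 has minimum and maximum reported for continuous data, a score outside 0–100 would appear in the table.

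**Working it through.** **Inputs.** 12 items; ratings 1 to 5; evaluable if k ≥ 9 items are answered; X = sum of ratings; Y = 100 × (X − 12)/48; no imputation. All come from SAP Section 5.2.1, except the imputation default, which is in SAP Section 5.

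**The plan's own example.** Twelve items rated 3: X = 36 and Y = 100 × 24/48 = 50, as the SAP states. The 12-item limits are 100 × (12 − 12)/48 = 0 and 100 × (60 − 12)/48 = 100. The formula is correct for complete forms.

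**Incomplete but evaluable forms.** With k items all rated r, X = k × r and Y = 100 × (k × r − 12)/48:

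| Items answered (k) | all rated 1 | all rated 3 | all rated 5 |
|---|---|---|---|
| 12 | 0 | 50 | 100 |
| 11 | −2.08 | 43.75 | 89.58 |
| 10 | −4.17 | 37.50 | 79.17 |
| 9 | −6.25 | 31.25 | 68.75 |

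For example, nine items rated 3 give X = 27 and Y = 100 × 15/48 = 31.25. The columns for ratings 1 and 5 are also the lowest and highest scores attainable for that k.

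**Loss per blank.** An item that would have been rated r takes r off X and 100 × r/48 off Y: 2.08 points for r = 1, 6.25 for r = 3 and 10.42 for r = 5.

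**Negative scores.** Y < 0 whenever X < 12. This is impossible with 12 items. It occurs with 11 items if X = 11, with 10 items if X is 10 or 11, and with 9 items if X is 9, 10 or 11.

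**Effect on change from baseline.**
- Stable patient at rating 3, complete at baseline, three blanks at follow-up: 31.25 − 50 = −18.75, when nothing changed. With the blanks at baseline instead, the result is +18.75.
- The same three items blank at both visits, answered items moving from 3 to 4: Y goes from 31.25 to 100 × (36 − 12)/48 = 50, a change of 18.75. Scored on the answered items, the change is 75 − 50 = 25. The plan's change is multiplied by 9/12.

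**Effect on a visit mean.** The documents give no rate of skipped items, so this is an assumption. If 5% to 20% of follow-up forms lack one item that would have been rated 3, and baseline forms are complete, the mean change shifts by −0.05 × 6.25 = −0.31 to −0.20 × 6.25 = −1.25 points.

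**Scoring on the answered items.** Let m be the mean answered rating. Setting X = 12 × m gives Y = 100 × (12m − 12)/48 = 100 × (m − 1)/4. For k = 9, 10, 11 or 12, ratings all 1, 3 or 5 then give 0, 50 and 100, and the score always stays within 0–100.

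**The case against.** The strongest reply is that the SAP nowhere says a blank counts as 0. It describes X as "as the sum of all the ratings on all the HRQoL questions for a single patient and the score can range from 12" up to 60, and a nine-item sum of 9 lies outside that range, so one could argue that X is defined only for complete forms. On that view a rule is missing but no score is wrong. The SAP also cites the instrument's publication, which may contain a missing-item rule, and some figures beside the CushingQoL text in Protocol Section 10.5.4 are not shown.

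This does not rescue the text. If X exists only for complete forms, the 9-item rule has no effect. An unseen rule is conjecture, and the SAP writes out its scoring steps without one. Protocol Section 10.5.4 does state what happens to WPAI-GH when an item is missing (the score is not calculated), but gives nothing comparable for CushingQoL. Zero for a blank is an inference, but it is what a plain sum without imputation produces.

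Several points on the other side do stand:
- The endpoint is descriptive. No hypothesis is tested, and neither the primary safety variable nor the sample size is affected.
- Negative scores need almost every answer to be the worst one, so they are a corner case.
- With plausible rates of skipped items, the shift in a visit mean may be small. Equal missingness at both visits largely cancels in the mean change, although the change is still shrunk in patients whose answers move.
- The values 0, 50 and 100 for incomplete forms are right only if the blank items would have been rated like the answered ones. Scoring by the patient's own mean is a reasonable choice, but not the only one.

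**Conclusion.** The concern holds. For every form with 9 to 11 answers, the stated rules give a score that is too low by 100 × r/48 for each blank, that is, 2.08 to 10.42 points on a 0–100 scale. Three blanks in a patient at mid-scale cost 18.75 points. Scores down to −6.25 are possible, though rare. Complete forms are scored correctly.

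The result rests on reading X as the sum of the ratings present, with no imputation. The only other reading makes the 9-item rule void, so the text needs correcting either way. The effect on the reported means depends on how often items are skipped and on whether that differs between baseline and follow-up; the documents do not say. The error for an individual patient does not depend on that rate. Because the plan as written gives a wrong within-patient change on a named secondary endpoint, it should be corrected before the analysis is run.

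**What to change.** Add one sentence to the scoring steps in SAP Section 5.2.1: when 9 to 11 items are answered, X is 12 times the mean of the answered ratings, equivalently Y = 100 × (mean answered rating − 1)/4; when fewer than 9 are answered, Y is missing. State the assumption that a patient's unanswered items resemble the answered ones. It is milder than the present implicit rating of 0.

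The cost is that sentence and one line of code. Scores for complete forms and the SAP's worked example stay as they are, and the 9-item rule in both documents becomes workable. Tabulating the number of answered items by visit would also show how many scores depend on the rule.

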5.3 Safety analyses

5.3.1 Analysis set and grouping for the analyses

For all safety analyses, the safety set will be used.

The overall observation period will be divided into three mutually exclusive segments:

1. Pre-treatment period: from day of patient's informed consent to the day before first dose of study medication,
2. On-treatment period: from day of first dose of study medication to 28 days after last dose of study medication,
3. Post-treatment period: starting at 29 days after last dose of study medication.

5.3.2 Adverse events

Summary tables for adverse events (AEs) will include only AEs that started or worsened during the on-treatment period, the **treatment-emergent** AEs. However, all safety data (including those from the pre and post-treatment periods) will be listed and those collected during the pre and post-treatment period will be flagged.

For the primary objective of the study, the number and percentage of patients having any drug-related adverse event that was recorded as grade 3 or 4, or as a serious adverse event will be summarized by system organ class and/or preferred term, severity (based on CTCAE grades), and type of adverse event.

In addition, the incidence of treatment-emergent adverse events (new or worsening from baseline) will be summarized by system organ class and/or preferred term, severity (based on CTCAE grades), type of adverse event and relation to study treatment. Deaths will be listed and summarized by cause of death.

The following adverse event summaries will be provided:

- Adverse events, suspected to be study drug related that was recorded as grade 3 or 4, or as a serious adverse event, by primary system organ class and/or preferred term and severity (based on CTCAE grades),

- Adverse events, regardless of study drug relationship, by primary system organ class and preferred term,
- Adverse events, suspected to be study drug related, by primary system organ class and preferred term,
- CTC grade 3 or 4 adverse events, regardless of study drug relationship, by primary system organ class and preferred term,
- CTC grade 3 or 4 adverse events, suspected to be study drug related, by primary system organ class and preferred term,
- Adverse events leading to study drug discontinuation, regardless of study drug relationship, by primary system organ class and preferred term,
- Deaths by primary system organ class and preferred term,
- SAEs, regardless of study drug relationship, by primary system organ class and preferred term,
- SAEs, suspected to be study drug related, by primary system organ class and preferred term,
- SAEs leading to study drug discontinuation, regardless of study drug relationship, by primary system organ class and preferred term.

For the legal requirements of ClinicalTrials.gov and EudraCT, two required tables on treatment-emergent adverse events which are not serious adverse events with an incidence greater than 2% and on treatment-emergent serious adverse events and SAE suspected to be related to study treatment will be provided by system organ class and preferred term on the safety set population. If for a same patient, several consecutive AEs (irrespective of study treatment causality, seriousness and severity) occurred with the same SOC and PT:

- a single occurrence will be counted if there is ≤ 1 day gap between the end date of the preceding AE and the start date of the consecutive AE
- more than one occurrence will be counted if there is > 1 day gap between the end date of the preceding AE and the start date of the consecutive AE

For occurrence, the presence of at least one SAE / SAE suspected to be related to study treatment / non SAE has to be checked in a block e.g., among AE's in a ≤ 1 day gap block, if at least one SAE is occurring, then one occurrence is calculated for that SAE.

The number of deaths resulting from SAEs suspected to be related to study treatment and SAEs irrespective of study treatment relationship will be provided by SOC and PT.

5.3.2.1 Grouping of adverse events of special interest

Specific groupings of adverse events of special interest will be considered and the number of patients with at least one event in each grouping will be reported. Such groups consist of adverse events for which there is a specific clinical interest in connection with pasireotide treatment (i.e. where pasireotide may influence a common mechanism of action responsible for triggering them) or adverse events which are similar in nature (although not identical) within project defined group. The specific groupings of AEs will be used and documented in CSR. For more detail please refer section 8.

The following adverse event summary will be produced:

- Adverse events of special interest, regardless of study drug relationship, by category, preferred term and maximum CTC grade.

5.3.3 Laboratory abnormalities

The summaries will include all laboratory assessments collected no later than 28 days after study treatment discontinuation. All laboratory data will be listed and those collected later than 28 days after study treatment discontinuation will be flagged in the listings.

For laboratory tests covered by the Common Terminology Criteria for Adverse Events (CTCAE) version 3.0, the study's biostatistics and reporting team will grade laboratory data accordingly. For laboratory tests covered by CTCAE, a Grade 0 will be assigned for all non-missing values not graded as 1 or higher. Grade 5 will not be used. In the unlikely case when a local laboratory normal range overlaps into the higher (i.e. non-zero) CTC grade, the laboratory value will still be taken as within normal limits and assigned a CTC grade of zero.

For laboratory tests where grades are not defined by CTCAE, results will be graded by the low/normal/high classifications based on laboratory normal ranges.

Concentrations below the limit of quantification will not be presented in summary statistics.

The following summaries will be produced for the laboratory data (by laboratory parameter)

- Shift tables using CTCAE grades to compare baseline to the worst on-treatment value,
- For laboratory tests where CTCAE grades are not defined, shift tables using the low/normal/high classification to compare baseline to the worst on-treatment value,
- Shift tables of fasting glucose and related biochemical parameters using the [ADA \(2010\)](#) or similar low/normal/high classifications to compare baseline to the worst and last on-treatment value.

The following listings will be produced for the laboratory data:

- Listing of patients with laboratory values outside the laboratory reference ranges with values flagged to show the corresponding CTC grades and the classifications relative to the laboratory reference ranges,
- Listing of all laboratory data with values flagged to show the corresponding CTCAE grades and the classifications relative to the laboratory normal ranges.

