To document the changes in patient-reported outcome questionnaires (CushingQoL and WPAI-GH)	The change from baseline to Week 12, 24 and 48 in CushingQoL and WPAI-GH scores	
To document the effects of pasireotide s.c. on the GH/IGF-I axis	The change from baseline to Week 12, 24 and 48 in GH and IGF-I separately	
To document the overall safety and tolerability of pasireotide s.c. in patients with CD	Incidence of AEs, and laboratory, vital signs and electrocardiographic abnormalities. Changes in laboratory values, electrocardiograms readings, and in vital signs values.	

4 Study design

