7.2.2.4.3 Clinical chemistry

The following tests will be performed at each scheduled visit as indicated in [Table 7-1](#): total proteins, amylase, lipase, total cholesterol (TC), LDL-cholesterol, triglycerides, sodium, potassium, magnesium, urea, serum creatinine, creatinine clearance, thyroid function test (free T4 and TSH), fasting blood glucose, fasting insulin, glycosylated hemoglobin (HbA_{1C}), and assessment of Vitamin B12, GH and IGF-1.

Liver function tests (LFT)

LFT will be performed at each scheduled visit as indicated in [Table 7-1](#) and will include ALT, AST, total bilirubin, albumin, ALP, and GGT.

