10.4.2 Statistical hypothesis, model, and method of analysis

No statistical hypotheses are being tested in this study.

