5.2 Secondary objectives

5.2.1 Efficacy objectives

These analyses will be performed on the FAS.

Mean 24h-UFC calculation

Screening urinary free cortisol will be measured in two or three 24-hour urine specimens collected during the screening period. The 24h-UFC concentration results from these two or three samples will be averaged to obtain the baseline UFC level. During the study, mean 24h-UFC will be determined at 4-week intervals until week 24. At week 4, 8, 16 and 20, mean 24h-UFC will be determined from two 24-hour urine collections collected on two consecutive days occurring before the visit. At week 12, 24 and 48, the mean 24h-UFC will be determined from two or three 24-hour urine collections, collected over the week before the visit. After week 24, the mean 24h-UFC will be determined at 12-week intervals until end of study visit, from two 24-hour collections during two consecutive days prior to each respective visit (except at Week 48).

Normalization of mean 24h-UFC at Week 12, 24 and 48

The endpoint associated with this objective is the proportion of patients achieving normalization of the mean 24h-UFC (UFC normalization), i.e. the mean 24h-UFC is $\leq 1.0 \times \text{ULN}$.

The number and percentage with corresponding two-sided 95% CI of patients achieving normalization of mean UFC mean 24h-UFC will be presented at Week 12, 24 and 48 (separately).

Note, the mean 24h-UFC is determined from two or three 24h-urine collections collected over the week before the visit.

Mean 24h-UFC imputation

If Week 24 mean 24h-UFC is missing then it will be imputed by the last available mean 24h-UFC values of at least two samples between and including Week 12 and Week 24. If Week 48 mean 24h-UFC is missing then it will be imputed by the last available mean 24h-UFC values of at least two samples between and including Week 12 and Week 48.

Summaries with and without imputing missing Week 24 and Week 48 mean 24h-UFC will be presented.

Similar analyses as defined above will also be performed at all other scheduled post-baseline assessments.

Reduction of mean 24h-UFC $\geq 50\%$ from baseline to Week 12, 24 and 48

The number and percentage with corresponding two-sided 95% CI of patients achieving a reduction of mean 24h-UFC $\geq 50\%$ from baseline to Week 12, 24 and 48 (separately) will be presented.

Similar analyses as defined above will also be performed at all other scheduled post-baseline assessments.

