. For example, if a patient answers all 12 items with 'Sometimes' or 'Somewhat', X = 36 and $Y = 100 \cdot 24/48 = 50$.

Similar analyses as defined above will also be performed at all other scheduled post-baseline assessments.

Changes from baseline to Week 12 , 24 and 48 in WPAI-GH scores

The WPAI-GH questionnaire is to assess work productivity and activity impairment.

WPAI outcomes are expressed as impairment percentages, with higher numbers indicating greater impairment and less productivity, i.e., worse outcomes, as follows (see [Reilly 2002](#)):

Questions:

- 1 = currently employed
- 2 = hours missed due to health problems
- 3 = hours missed other reasons
- 4 = hours actually worked
- 5 = degree health affected productivity while working
- 6 = degree health affected regular activities

Scores (multiply scores by 100 to express in percentages):

Percent work time missed due to health: $Q2/(Q2+Q4)$

Percent impairment while working due to health: $Q5/10$

Percent overall work impairment due to health:

$Q2/(Q2 + Q4)+[(1 - Q2/(Q2 + Q4)) \cdot (Q5/10)]$

[figure not shown]
Percent activity impairment due to health: $Q6/10$

Descriptive summaries of actual and percentage change in mean scores from baseline to Week 12, 24 and 48 will be provided. Similar analyses will also be performed at all other scheduled post-baseline assessments.

Changes from baseline in GH and IGF-I to Week 12, 24 and 48

Descriptive summaries of the absolute and relative change from baseline of GH and IGF-I at Week 12, 24 and 48 will be provided.

Similar analyses will also be performed at all other scheduled post-baseline assessments.

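### SAP 5.3.3 drops results below the limit of quantification (LOQ) from summary statistics, with no substitution or planned count, and does not say whether the GH and IGF-I change summaries are covered

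*SAP*

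**What the plan says.** SAP 5.3.3 (Laboratory abnormalities) sets the rule: "Concentrations below the limit of quantification will not be presented in summary statistics". It is the only statement about LOQ in either document. It names no parameters and no substituted value, and it plans no count of removed results. The parallel Protocol section, 10.5.2.3, has no such rule.

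The opening of SAP section 5 fixes the statistics: "For continuous data, mean, standard deviation, median, minimum, and maximum will be presented". SAP 4.4 (Visit windows) sets out how assessments are chosen for summary tables of all laboratory data, so visit-level laboratory summaries are planned. Neither place mentions LOQ, and nor does SAP section 7 (Data handling conventions).

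GH and IGF-I change is a secondary endpoint in Protocol Table 3-1: "The change from baseline to Week 12, 24 and 48 in GH and IGF-I separately". SAP 5.2.1 repeats the plan without an LOQ rule: "Descriptive summaries of the absolute and relative change from baseline of GH and IGF-I at Week 12, 24 and 48 will be provided". Protocol 7.2.2.4.3 lists the two hormones among the clinical chemistry tests ("assessment of Vitamin B12, GH and IGF-1").

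**The concern.** A below-LOQ result is not missing. It says that the concentration was low, with an upper bound. Leaving it out removes patients from the table because of the value that the table is meant to describe.

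This matters most for an analyte that falls on treatment. More results then drop below LOQ after baseline than before it, so the patients removed are disproportionately those with the lowest on-treatment values. With no planned count, a reader of the table could not tell how many were removed.

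If the rule reaches GH and IGF-I, a named secondary endpoint is summarised on a selected sample. If it does not, that endpoint has no below-LOQ rule and the choice is left to programming.

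**Working it through.** **No figure to reproduce.** The plan gives no LOQ, below-LOQ rate, variability or expected change. The numbers below are illustrations under stated assumptions.

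**Step 1: levels, without assumptions.** Every removed value is lower than every retained value. If at least one value is removed and at least one kept, the displayed mean and minimum must rise, and the median cannot fall.

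**Step 2: levels, lognormal.** Let a share q be below LOQ at a visit. The median of what remains is the original (1+q)/2 quantile, so

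displayed median / true median = exp(SD × z((1+q)/2)),

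with SD on the log scale. For q = 1%, 5%, 15%, z = 0.0125, 0.0627, 0.1891.
- Log-SD 1.0: too high by 1.3%, 6.5%, 20.8%.
- Log-SD 0.4: too high by 0.5%, 2.5%, 7.9%.

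**Step 3: share below LOQ on treatment.** With the same LOQ at both visits and a true 50% fall, the share is Φ(z(q) + ln 2 / SD). For q = 15% at baseline:
- log-SD 1.0: Φ(-1.036 + 0.693) = 36.6%;
- log-SD 0.4: Φ(-1.036 + 1.733) = 75.7%.

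**Step 4: change from baseline.** Simulation of 2,000,000 lognormal pairs, dropping any pair with a value below LOQ. Median relative change (%) when the truth is -50%, by share below LOQ at baseline:

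| Log-SD | Correlation | 1% | 5% | 15% |
|---|---|---|---|---|
| 0.4 | 0.3 | -43.6 | -37.5 | -31.0 |
| 0.4 | 0.6 | -46.3 | -42.9 | -38.9 |
| 0.4 | 0.8 | -48.1 | -46.4 | -44.6 |
| 1.0 | 0.3 | -47.2 | -42.1 | -35.0 |
| 1.0 | 0.6 | -48.2 | -45.0 | -40.5 |
| 1.0 | 0.8 | -49.0 | -47.2 | -44.6 |

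A wider grid used log-SD 0.4, 0.8, 1.0, 1.2; the same correlations and shares; and true falls of 20% and 50% (4 × 3 × 3 × 2 = 72 scenarios). The median relative fall was understated in all 72.

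**Step 5: mean absolute change has no fixed direction.** In the same 72 scenarios the mean absolute fall was overstated by more than 0.5% in 60, within 0.5% in 4, and understated by more than 0.5% in 8, with a range of -17% to +36%. Dropping pairs that were already low at baseline removes small absolute falls. Dropping pairs that fell from a high baseline to below LOQ removes large ones. Either can dominate; understatement appears when spread is small and correlation low.

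**Step 6: no true change.** The median relative change and mean absolute change are unaffected. The mean relative change still moves towards zero: at log-SD 1.0 and correlation 0.6 it is +49% on all data, and +48%, +44% and +39% under the rule at 1%, 5% and 15%.

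**Step 7: does the rule reach GH and IGF-I?**
- For: both are clinical chemistry tests; 5.3.3 itself names only shift tables and listings, so a rule on summary statistics would seem to look beyond that section; and 5.2.1 has no rule of its own.
- Against: 5.2.1 is the efficacy section ("These analyses will be performed on the FAS"), 5.3 is the safety section ("For all safety analyses, the safety set will be used"), and neither refers to the other on this point.

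The text does not settle it.

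**The case against.** The strongest reply is that no affected output is shown beside the rule. The outputs named in 5.3.3 are shift tables and listings, and GH and IGF-I are summarised elsewhere on a different analysis set. This stands in part. Reach to 5.2.1 is an inference, and a reader who takes it as settled goes further than the documents do. But SAP 4.4 plans summary tables for all laboratory data, so the rule has something to act on whichever way the GH question falls. The SAP also does not say whether shift tables count as summary statistics; if they do, the lowest results would leave the low category.

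Second, the size is unknown and may be zero. That stands in full. The 20% and 50% falls are assumptions, and some scenarios are extreme, such as the one with about 76% below LOQ on treatment.

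Third, the SAP is silent on counts but does not forbid them, and table shells are not among the documents. That also stands, so the point is that no count is planned. All values are listed, so removed results can be traced.

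Two stronger readings are tempting. A reader might infer that the rule always understates the drug's effect; Step 5 shows that this fails for the mean absolute change. A reader might also infer that the maximum is always safe. That is true of levels, but the maximum relative change can fall when a pair with a very low baseline is dropped.

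**Conclusion.** The point holds as a minor one. For any laboratory summary it governs, the rule makes displayed levels and the minimum too high whenever a value is below LOQ. It understates the median relative fall of an analyte that truly falls. Under the assumptions of Step 4, a true 50% fall is shown as about -44 to -49% with 1% below LOQ at baseline, -38 to -47% with 5%, and -31 to -45% with 15%. These figures rest on lognormal data, one LOQ at both visits, log-SD 0.4 or 1.0 and correlation 0.3 to 0.8, none of which comes from the documents.

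Whether GH and IGF-I are affected is open, and either answer needs a line in the SAP. The consequence is limited: Protocol 10.4.2 states "No statistical hypotheses are being tested in this study", the primary variable is an adverse-event proportion, and only descriptive summaries change.

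**What to change.** Replace the sentence in SAP 5.3.3 with:

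*Values below the LOQ are retained in summary statistics; they are ranked lowest for the median and shown as below LOQ where they are the minimum or median. The number of values, and the number and percentage below LOQ, are shown at baseline and at each visit. This also applies to GH and IGF-I in Section 5.2.1.*

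For means and changes from baseline, prespecify one substituted value (for example LOQ/2) and a second (for example LOQ) as a sensitivity check. Count pairs with both values below LOQ and report them separately, since substitution would give them an artificial 0% change. Setting them apart is itself a selection on the value, so their number must be shown.

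The cost is one paragraph, a simple derivation and an extra line per affected table.

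The downside is that the substituted value is arbitrary. At log-SD 1.0, correlation 0.6 and a true 50% fall, the two values give medians of -50.6 and about -49.4% with 1% below LOQ at baseline, but -56.1 and -43.4% with 15%. LOQ/2 can also do worse than the present rule: with no true change, log-SD 0.4, correlation 0.6 and 15% below LOQ, it gives a mean relative change of +14.3%, against +6.6% on all data and about +5.5% under the rule. The counts and medians should therefore be read first.
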